| 14 Ethics/Protection of Human Subjects..... | 36 |
| 14.1 Ethical Standard | 36 |
| 14.2 Institutional Review Board | 36 |
| 14.3 Informed Consent Process | 36 |
| 14.3.1 Informed Consent/Accent Process (in Case of a Minor) | 36 |
| 14.4 Exclusion of Women, Minorities, and Children (Special Populations) | 36 |
| 14.5 Participant Confidentiality | 37 |
| 14.7 Study Discontinuation | 37 |
| 14.8 Future Use of Stored Specimens | 37 |
| 15 Data Handling and Record Keeping..... | 39 |
| 15.1 Data Management Responsibilities | 39 |

Table of Contents - *continued*

| | page |
|--|-------------|
| 15.2 Data Capture Methods | 39 |
| 15.3 Types of Data | 40 |
| 15.4 Timing/Reports | 40 |
| 15.5 Study Records Retention..... | 40 |
| 16 Publication Policy..... | 41 |
| 17 Literature References..... | 42 |
| 18 Supplement/Appendices..... | 43 |

List of Abbreviations

| | |
|-------|--|
| AE | Adverse Event |
| ASCs | Antibody Secreting Cells |
| CFR | Code of Federal Regulations |
| CEIRS | Center for Influenza Excellence in Research and Surveillance |
| CoC | Certificate of Confidentiality |
| CRF | Case Report Form |
| DMID | Division of Microbiology and Infectious Diseases, NIAID, NIH |
| eCRF | Electronic CRF |
| FDA | Food and Drug Administration |
| GCP | Good Clinical Practice |
| HA | Hemagglutinin |
| HHS | Health and Human Services |
| HI | Hemagglutination Inhibition |
| HIPAA | Health Insurance Portability and Accountability Act |
| ICH | International Conference on Harmonisation |
| IMGT | Immunogenetics Information System |
| IM | Intramuscular |
| IRB | Institutional Review Board |
| ml | Milliliter |
| MOP | Manual of Procedures |
| NA | Neuraminidase |
| NGS | Next Generation Sequencing |
| NIAID | National Institute of Allergy and Infectious Diseases, NIH |
| NIH | National Institutes of Health |
| PHI | Protected Health Information |
| SAE | Serious Adverse Event |
| SMC | Safety Monitoring Committee |
| TIV | Trivalent Inactivated Vaccine |
| US | United States |
| VAERS | Vaccine Adverse Event Reporting System |
| WCI | Winship Cancer Institute |
| WNL | Within Normal Limits |

Protocol Summary

Title: Analysis of Bone Marrow and Blood B cell Immune Responses to Influenza Vaccination

Population: Male and female individuals aged 18-49 years.

Number of Sites: 1

Study Duration: 4 years

Participant Duration: 365 days (1 year) – 1095 days (3 years)

Objectives:

Primary Objective: To investigate the longevity of humoral immunity to influenza virus in humans.

Secondary Objectives: Longitudinal tracking of vaccine-induced B cell responses with special emphasis on broadly neutralizing HA stem reactive responses.

[figure not shown]
Study Summary:

This is a Phase IV open label and single arm observational study enrolling up to 55 healthy males and non-pregnant females, 18-49 years old, inclusive. The study is designed to assess the humoral response to influenza vaccination and the longevity of humoral immunity to influenza vaccination in healthy adults. The laboratory technique will characterize persistence and clonotype of antigen specific B-cells and plasmablasts in blood and bone marrow. Enrolled subjects will receive licensed seasonal inactivated influenza vaccine (administered as a part of the study). The vaccine will be administered according to the package insert, and study participants will donate serial samples of blood and bone marrow aspirate for immunology monitoring. Safety will be assessed from the time of study enrollment through the last study visit, via monitoring of vital signs, change in health status, and targeted physical exam with safety labs prior to each bone marrow aspirate procedure. Repeated measurements of humoral immunity will be obtained at 7 days, 14 days, 28 days, 90 days and at one year post vaccination to assess the magnitude, clonal diversity and persistence of B-cell responses to influenza vaccination.

Due to the COVID-19 pandemic, all non-essential research was halted in mid-March 2020. New enrollments were placed on hold for this study. Follow-up visits were also halted, which impacted the timing of participants' subsequent follow-up visits. For this study, there are participants whose Day 28 and Day 90 visits were impacted by the temporary halting of non-essential research studies. We will request an expansion of the study window for the participants whose visits were impacted. Additional details regarding this are detailed further in the protocol. None of the other timepoint visits were impacted. Dependent upon Emory's guidelines in response to the evolving nature of the pandemic and the prioritization of studies being allowed to re-open, time will be

needed to secure the appropriate approvals and clearance to bring research participants back for their missed visits. As such, we would like to request that the missed visit windows for the Day 28 and Day 90 visits be extended for a maximum of up to 180 days, to ensure that ample time is available to bring participants back for their missed visits. Enrollment for this study ended on March 31, 2020.

Subjects will be offered the opportunity to participate in the study for up to 3 consecutive years provided eligibility criteria is met each year. Subjects who elect to continue in the study after first year of participation will be rescreened to verify continued eligibility and re-consented prior to subsequent participation. Re-enrolling subjects will receive new subject identifiers and will count towards the total enrollment number for subsequent years of participation. A separate subject record will be maintained each year a subject re-enrolls in the study.

Schematic of Study Design:

| Subjects enrolled in study | Years study performed | Number of subjects per year (study total) | Blood or Bone Marrow samples (days post-influenza vaccination) |
|------------------------------|-----------------------|--|---|
| Healthy adults (18-49 years) | Years 1-4 | Years 1-3: 15/year Year 4: 10 (Total: 55) | Blood volume 64ml per visit (320 ml total)– Day: 0, 7, 14, 28, 90, 365* Bone marrow aspirate volume 30 ml per visit (90ml total)– Day: 0, 28, 365* |

* Subjects that consent to be in the study for subsequent years, the “Day 0” of the second and third years will constitute “day 365” and “day 730” with respect to the first year of participation.

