- **Day 28 post vaccination study visit (+/- 2 days):** Subjects will have clinical safety labs drawn including a platelet count and hemoglobin and hematocrit (4ml of blood) Females of childbearing potential will have a urine pregnancy test performed, and the test result must be negative for the subject to continue with study participation. The results of the blood tests must be assessed by the study physician as within a healthy range for continued study participation using the most current normal lab ranges, and evaluated for clinical significance of lab values that fall outside of normal range. Subjects will have 64 ml of blood drawn for antibody testing. Vital signs including oral temperature, blood pressure, pulse rate and respiratory rate will be obtained. A health assessment will be performed including an inquiry about any illness or health change since the last study visit. Concomitant medications will be reviewed and updated. An assessment will be made for any adverse events or serious adverse events. Participants will receive a physical exam by a licensed to make medical diagnoses and listed on the Investigator of Record Form as the site principal investigator or sub-investigator. The Adverse Event Report Form will be updated if indicated. Study eligibility criteria will be reviewed by the study nurse and physician and confirmed that the subject meets all inclusion and none of the exclusion eligibility criteria prior to the bone marrow aspirate procedure. [name] as site principal investigator or the sub-investigator will explain the bone marrow aspirate procedure, and the informed consent document for the procedure will be signed by the subject in the presence of [name]. The bone marrow aspirate procedure and aspirate volume will be the same as the same as at study enrollment.
 - Due to the COVID-19 pandemic, all non-essential research was halted in mid-March 2020.
 - One participant had their Day 28 visit halted.
 - We are requesting that the Day 28 window be extended by a maximum of up to 180 days, to allow completion of the follow-up visit for the impacted participant.
 - The participant will be contacted by phone or via encrypted email message to arrange scheduling of subsequent visits.
 - To assist with assessing symptoms, the COVID-19 Screening Questionnaire/Script will be reviewed with participants prior to bringing the participant in for follow-up visits.

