- **Day 90 visit (acceptable range: days 80-120):** Subjects will have 64 ml of blood drawn for antibody testing. Vital signs including oral temperature, blood pressure, pulse rate and respiratory rate will be obtained. A health assessment will be performed including an inquiry about any illness or health change since the last study visit as well as change in concomitant medication. Medical history will be reviewed and updated with any reported changes. An assessment will be made for any adverse events or serious adverse events. The Adverse Event Report Form will be updated based on the subject's self-report.
 - Three participants had their Day 90 visit halted due to the COVID-19 pandemic.
 - We are requesting that the Day 90 window be extended by a maximum of up to 180 days, to allow completion of the follow-up visits for impacted participants.
 - Participants will be contacted by phone or via encrypted email message to arrange scheduling of subsequent visits.
 - To assist with assessing symptoms, the COVID-19 Screening Questionnaire/Script will be reviewed with participants prior to bringing them in for follow-up visits.

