9.4 Type and Duration of Follow-up of Participants after Adverse Events

Clinical studies at Emory University are compliant with ICH E6 guidelines for Good Clinical Practice.

Adverse events will be documented and reported according to the DMID and Emory IRB policies (as described in section 9.2.1 and 9.3). All AEs and SAEs will be followed until resolved, return to baseline or stable as determined by the study team. The occurrence of AEs and the status of existing AEs will be assessed at each study visit and events are recorded in the regulatory binder. Subjects will be encouraged to contact study staff of any health changes that may occur between study visits. An unscheduled visit or telephone follow-up may occur depending on the adverse event.

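### No adverse-event inquiry is scheduled after the final Day 365 bone marrow aspirate of a participant who does not re-enroll, and the Day 28 aspirate waits 50 to 94 days for one

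*Combined protocol and SAP*

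**What the plan says.** Bone marrow is aspirated on Days 0, 28 and 365 (Protocol Summary; Appendix A). The Study Summary sets the safety period: "Safety will be assessed from the time of study enrollment through the last study visit". Section 9.4 ties inquiry to visits: "The occurrence of AEs and the status of existing AEs will be assessed at each study visit". Appendix A marks the adverse-event row at every visit and shows no contact between visits.

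Section 7.3 includes an adverse-event check at the Day 28 and Day 365 visits: "An assessment will be made for any adverse events or serious adverse events". Later in each visit description, staff review eligibility and it is "confirmed that the subject meets all inclusion and none of the exclusion eligibility criteria prior to the bone marrow aspirate procedure". Day 28 has a window of plus or minus 2 days. The next visit is described as "Day 90 visit (acceptable range: days 80-120"), and its adverse-event form is updated from self-report. Day 365 ends participation unless the participant re-enrolls, in which case it may double as the new Day 0.

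Between visits, Section 9.4 relies on the participant: "Subjects will be encouraged to contact study staff of any health changes that may occur between study visits". Section 7.5 allows unscheduled visits but does not expect them. Section 9.3.1 collects serious adverse events until study completion or withdrawal, with reporting within 24 hours of site awareness.

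On the COVID-19 interruption, Section 7.3 reports: "One participant had their Day 28 visit halted", and adds: "We are requesting that the Day 28 window be extended by a maximum of up to 180 days". Three participants had their Day 90 visit halted, with an extension of the same length requested.

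**The concern.** The aspirate is the most invasive procedure in the study, and Section 2.3.2 says that it brings the volunteers no benefit. Sections 2.3.1 and 9.2.1 list its expected effects: pain and bruising for 1 to 3 days, mild anemia for one to two weeks and, very rarely, infection or damage to vessels or bone. Section 9.2.1 limits reportable adverse events to those associated with study procedures outside normal care. Procedure-related events are thus the ones the safety plan most needs to capture.

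Only an aspirate on Day 0, or on a Day 365 that is also a new Day 0, is followed by a scheduled visit within about a week (Day 7). After a final aspirate, a procedure-related event that does not lead to hospital admission may never be recorded unless the participant volunteers it. Section 9.5 halts the study for a procedure-related serious event or for two similar severe procedure-related events, and the independent safety monitor (Section 9.6.1) can review only what the site knows. An event that is not elicited cannot count while other participants may still be having aspirates.

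**Working it through.** The plan states no interval from aspirate to next inquiry, so there is no figure of its own to reproduce. The inputs are the visit windows in Section 7.3 and the enrollment slots in Section 5.

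**Final Day 365 aspirate, no re-enrollment.** The aspirate takes place at the last visit, and safety assessment runs through the last visit. Scheduled inquiries afterwards: 0.

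**Day 28 aspirate, standard windows.** Aspirate on Days 26–30 (28 ± 2); next inquiry on Days 80–120.
- Shortest gap: 80 − 30 = 50 days.
- Nominal gap: 90 − 28 = 62 days.
- Longest gap: 120 − 26 = 94 days.

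**COVID-extended Day 90 visits.** The longest gap depends on how the 180-day limit is read, taking an aspirate on Day 26:
- limit means Day 180: 180 − 26 = 154 days;
- 180 days added to Day 90: 270 − 26 = 244 days;
- 180 days added to Day 120: 300 − 26 = 274 days.

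The documents do not settle the reading. Nor do they say whether the participant with the halted Day 28 visit is one of the three with a halted Day 90 visit; for that person these figures would not apply.

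**Pending Day 28 aspirate.** If 180 days are added to the nominal day or to the end of the window, it could fall as late as 28 + 180 = Day 208 or 30 + 180 = Day 210. The order of this participant's delayed Day 28 visit and Day 90 visit is not stated, so the time to the next inquiry cannot be fixed.

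**Share of aspirates that are final.** Slots: 15 + 15 + 15 + 10 = 55. Assume full enrollment and follow-up.
- No re-enrollment: 55 × 3 = 165 aspirates, of which 55 are final. 55/165 = 33%.
- Maximum re-enrollment: with at most three consecutive years, nobody can fill both a Year 1 and a Year 4 slot, so there are at least 15 + 10 = 25 persons. That leaves 55 − 25 = 30 re-enrollments. If each shares its Day 365 aspirate with the new Day 0, there are 165 − 30 = 135 aspirates, of which 25 are final. 25/135 = 19%.

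**The case against.** **The gap may be closed elsewhere.** Section 7.2 has the aspirate done under an institutional procedure. That procedure and the Manual of Procedures are not available here, the consent pages were removed, and the Appendix B chart is not shown. Any of these could require a follow-up call. This stands as a limit on the finding, and the fix allows for it.

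**Serious events may be covered for longer.** A reader might infer that all collection stops at the last visit. The documents do not establish that: study completion in Section 9.3.1 could mean the whole study rather than one person's participation. Even so, this collection is passive, as are the encouragement to call and the unscheduled visit. Each starts only once someone brings the event to the site.

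**The same-day check might follow the aspirate.** A reader might infer from the order of the visit text that adverse events are assessed before the aspirate. Only the eligibility review is explicitly placed before it. The point does not need that inference, because a same-day check cannot see effects that develop over days or weeks.

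**The effect on halting is speculative.** Section 9.2.1 describes severe events as usually incapacitating, and a volunteer so affected would probably tell someone. Airway reactions or anaphylaxis within 72 hours would probably show on site or lead to care. This largely stands: the halting rules are less well fed, but nothing shows that they would fail.

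**After Day 28 the loss is mainly time.** The Day 90 visit can still record onset and resolution. This stands.

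**Conclusion.** The point holds as a surveillance gap that is cheap to close. For participants who do not re-enroll, the visible plan schedules no inquiry after the last aspirate. At full enrollment and follow-up this concerns 19% to 33% of aspirates, depending on re-enrollment. After the Day 28 aspirate the wait is 50 to 94 days under the standard windows and can be longer with an extended Day 90 visit, by an amount that depends on how the extension is read. There the cost is mainly delayed awareness and recall.

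A reader might pool the two and say that (55 + 25)/135 = 59% to (55 + 55)/165 = 67% of aspirates lack follow-up. The documents do not support that, because Day 28 aspirates are followed up, only late. Nor do they support any claim that events were missed or participants harmed, since no event rate is given.

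The conclusion assumes that no document outside the visible text already requires a post-procedure contact.

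**What to change.** In Section 7.3 and Appendix A, add one scripted telephone or e-mail check for adverse and serious adverse events about 14 days after each final Day 365 aspirate, and preferably also after the pending Day 28 aspirate if it goes ahead. Fourteen days spans the longest duration that the protocol gives for an expected aspirate effect. Extend adverse-event and serious-adverse-event collection to that contact in Section 9.3, and amend the Study Summary sentence to match. A call cannot measure anemia, so let symptoms trigger the unscheduled visit of Section 7.5, with its optional hematology sample. A further call at about day 3 is optional. Nothing is needed after Day 0, or after a Day 365 aspirate that is also a new Day 0. If the institutional procedure or the Manual of Procedures already requires such a contact, cite it in Section 7.3 instead.

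The cost is protocol wording and a few minutes per contact for staff who already use telephone and e-mail (Sections 7.3 and 7.4), plus a slightly higher recorded adverse-event count. Enrollment ended on March 31, 2020, and re-enrollment counts as enrollment (Section 4); on that reading every remaining Day 365 aspirate is final. The protocol does not say how many remain. Assuming 10 (Year 4 slots) to 25 (Year 3 and Year 4 slots, 15 + 10), one contact each plus one for the pending Day 28 aspirate makes 10 + 1 = 11 to 25 + 1 = 26 contacts. Endpoints, sampling and halting criteria stay as they are.

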2 BACKGROUND INFORMATION AND SCIENTIFIC RATIONALE

2.1 Background Information

Annual influenza virus epidemics by subtype A viruses (H1N1 and H3N2), and/or influenza B viruses have been shown to cause substantial morbidity and mortality, exacting an average of 36,000 deaths and more than 200,000 hospitalizations in the US alone (1).

To combat this important public health threat, two types of inactivated influenza vaccines have been approved by the FDA: 1) a trivalent, inactivated vaccine (TIV); and 2) a quadrivalent inactivated vaccine (QIV). The TIV vaccine contains the hemagglutinin (HA) and neuraminidase (NA) proteins corresponding to the three influenza viruses predicted to be in circulation during the influenza season (two A strains and one B), and the quadrivalent type contains the HA and NA for an additional B strain. These vaccines induce predominantly HA-specific and NA-specific antibodies that are capable of virus neutralization. Antibodies to HA are critical to provide immune protection to the host against influenza virus infection, as this protein plays a key role in virus entry to initiate the replication cycle in the cell. A live attenuated vaccine has also been approved but this study will use only inactivated influenza vaccine.

Currently, the Advisory Committee on Immunization Practices of the CDC recommends that everyone aged 6 months or older in the United States receive the influenza vaccine on an annual basis (2). The recommendation for annual vaccination, regardless of previous vaccination history, is in part due to the constantly changing nature of the influenza strains in circulation. Through the processes of antigenic drift and antigenic shift, the viral HA protein is constantly changing to evade the antibody response. This requires that the formulation of the influenza vaccine must be updated each season. However, when the vaccine formulation remains unchanged from year to year, re-vaccination is still recommended because antibody levels decline over the course of a year (3).

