5 STUDY POPULATION

Up to 55 subjects will be enrolled from the existing population of healthy adults residing in the Atlanta, Georgia area within the Emory University, Children's Healthcare of Atlanta, and Centers for Disease Control Clifton Road community. We plan to enroll 15 subjects per year for 3 years and 10 subjects in year 4. Re-enrolling subjects in subsequent second and third years will count towards the yearly enrollment totals for those years.

Males and non-pregnant females aged 18 - 49 inclusive. Pregnancy status will be verified at screening, enrollment and prior to all bone marrow aspiration procedures. Women of childbearing potential will be asked to use a barrier method of birth control or an FDA approved form of birth control.

Study subjects will be recruited via word of mouth and through placement of flyers in key locations on campus. Social media messaging via Facebook and Twitter will also be used in an effort to increase the number of enrollees into this study. Based on previous experience, we anticipate enrollment of 40 to 50 percent non-pregnant females on the study.

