5.1 Inclusion Criteria

For inclusion into the study, a subject must satisfy all of the following criteria:

1. Male or non-pregnant female subjects between 18 and 49 years of age (inclusive)
2. Subjects capable of providing written informed consent prior to initiation of any study procedures.
3. Subjects able to understand and comply with planned study procedures and be available for all study visits.
4. Safety labs
 - a. WBC, within reference range of lower limit of normal of 4,000/uL, and upper limit of normal of 10,000/uL.
 - b. Hemoglobin, within reference range of lower limit of normal of 11.4 gm/dL and upper limit of normal of 16.1 gm/dL.
 - c. Hematocrit, within reference range of lower limit of normal of 33.3% and an upper limit of normal of 46.5%.
 - d. Platelet Count within reference range of lower limit of normal of 150,000/uL and upper limit of normal of 400,000/uL.
 - e. PT/INR, PT below or equal to the upper limit of normal of 13.1 seconds; INR within normal reference range of less than 1.5 (normal range for non-anti-coagulated patients).
 - f. Creatinine within reference range of lower limit of normal of 0.4 mg/dL and upper limit of normal of 1.2 mg/dL.

- g. Potassium), within reference range of lower limit of normal of 3.6 mM and upper limit of normal of 5.1 mM.
5. Heart rate ≥ 55 to ≤ 100 per minute
6. Systolic blood pressure ≥ 90 to ≤ 150 mm Hg
7. Diastolic blood pressure < 90 mm Hg
8. Oral temperature $< 100^{\circ}\text{F}$
9. Respirations even, unlabored, and $> 10/\text{minute}$ to $< 20/\text{minute}$.
10. Female subjects of child bearing potential must have a negative urine pregnancy test at the screening visit, enrollment visit and prior to subsequent bone marrow aspirate procedures. Female subjects of childbearing potential must agree to practice abstinence, use a barrier method of birth control, or use an FDA approved form of birth control
11. Subjects who have not received seasonal flu vaccine for the current year (September – June)

Subjects that have participated in a previous year may be screened for re-enrollment in subsequent second and third year. Subjects that are re-enrolling will be re-consented, re-screened, and given a new identifier. Re-enrolling subjects will be counted towards the enrollment totals for each year. Subjects who report having already received the flu vaccine for the current flu season will be restricted from further study participation.

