- **Day 365 visit (+/- 3 months):** Subjects will have clinical safety labs drawn including a platelet count and hemoglobin and hematocrit (4ml of blood). Females of childbearing potential will have a urine pregnancy test performed, and the test result must be negative for the subject to continue with study participation. The results of the blood tests must be assessed by the study physician to be within a healthy range for continued study participation using the most current normal lab ranges, and evaluated for clinical significance of lab values that fall outside of normal range. Subjects will have 64 ml of blood drawn for antibody testing. Vital signs including oral temperature, blood pressure, pulse rate, and respiratory rate will be obtained. A health assessment will be performed including an inquiry about any illness or health change since the last study visit. Concomitant medications will be reviewed and updated. An assessment will be made for any adverse events or serious adverse events. Participants will receive a physical exam by a licensed to make medical diagnoses and listed on the Investigator of Record Form as the site principal investigator or sub-investigator. The Adverse Event Report Form will be updated if indicated. Study eligibility criteria will be reviewed by the study nurse and physician and confirmed that the subject meets all inclusion and none of the exclusion eligibility

criteria prior to the bone marrow aspirate procedure. [name] will explain the bone marrow aspirate procedure, and the informed consent document for the procedure will be signed by the subject in the presence of [name]. The bone marrow aspirate procedure and aspirate volume will be the same as the as at study enrollment and at visit day 28.

- It is not anticipated that any of the Day 365 visits will be impacted.

The day 365 post vaccination visit will be the final study visit unless the subject decides to re-enroll in the study. Provided eligibility criteria are met, subjects may re-enroll in the study for a total study participation of up to three years per subject. The day 365 visit may also be the day 0 visit for a subject who is re-enrolling into the study, provided that re-screening of the subject occurs and the subject meets study eligibility criteria for continued study participation. These subjects will receive a new study identifier and a separate research record will be maintained by study staff.

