11.2 Sample Size Considerations

A major goal our study is to understand the longevity of plasma cell responses directed against different determinants in the influenza vaccine. Our preliminary data has suggested that plasma cell clonal responses against conserved epitopes may be smaller in number and less prone to persist compared to responses against epitopes which are unique to the particular hemagglutinin strains used in the current year's vaccine. Our deep sequencing data suggests that after one year the frequency of the average vaccine-induced clone in the bone marrow is approximately 33% of the frequency observed at one month. However, there is a large variability in this maintenance (standard deviation of 44%). The small number of cross-reactive clones we have tracked so far have been undetectable after one year, suggesting that their maintenance is substantially lower than the average clone. We wish to be 80% confident in being able to detect whether the maintenance of these cross-reactive clones is at least 3-fold lower than for the average clone (i.e. 11% maintenance vs. 33%) with a P-value less than 0.05. This will require the longitudinal tracking of at least 25 broadly cross reactive plasma cell clones in our patient cohort. Our initial data suggests that we should be able to identify a single broadly cross-reactive clonotype in approximately 50% of our donors, meaning that a sample size of 50 donors will be required to follow 25 cross-reactive clonotypes. With our planned sample size of 55 donors, this allows for a potential dropout rate of 10%.

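### The 55 donors of section 11.2 are yearly enrolments that can count one person up to three times; the head count, the unit of the 50% clone yield and a person-level analysis rule are not stated

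*Combined protocol and SAP*

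**What the plan says.** **Sample size.** Section 11.2 wants 80% power to show that one-year maintenance of cross-reactive clones is 11% against 33% for the average clone (SD 44%), and concludes that 25 such clones must be followed. It expects that "we should be able to identify a single broadly cross-reactive clonotype in approximately 50% of our donors", which gives 50 donors, and adds: "With our planned sample size of 55 donors, this allows for a potential dropout rate of 10" per cent. The Study Summary also describes the 55 as people: "enrolling up to 55 healthy males and non-pregnant females".

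**Counting rule.** The design schematic and section 5 build 55 from 15 enrolments in each of years 1 to 3 and 10 in year 4. A person may take part for up to three consecutive years. The Protocol Summary and section 4 state: "Re-enrolling subjects will receive new subject identifiers and will count towards the total enrollment number for subsequent years of participation". Section 5 says: "Re-enrolling subjects in subsequent second and third years will count towards the yearly enrollment totals for those years". Section 5.1 says: "Re-enrolling subjects will be counted towards the enrollment totals for each year". On records, section 7.3 says: "These subjects will receive a new study identifier and a separate research record will be maintained by study staff".

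**Analysis.** Section 11.4 compares strain-specific and cross-reactive clones with an unpaired t-test and no term for the person. Section 11 plans general linear mixed models for differences among time points, without naming the person as the unit and without applying them to the clone comparison.

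**The concern.** Section 11.2 uses the word donor for what the enrolment rules define as a person-year slot. No section gives the expected number of distinct people, caps re-enrolment, or says whether the 50% yield is per person or per enrolment. The last omission decides what goes wrong.

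- If the yield is per person, a returning person fills a slot without adding an expected clone, and the 25-clone target is missed.
- If each enrolment can add a clone, the target count survives, but several clones come from one person and the planned test treats them as independent.

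This is the protocol's only sample-size statement. If the clone count falls short, a non-significant result would be read as more informative than it is. If clones are clustered, the standard error of the planned comparison is wrong. The new identifier and separate record each year also mean that, without an explicit link, one person could enter any analysis as up to three subjects. That includes the seroconversion percentages among the primary outcomes in section 3.2.1.

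**Working it through.** **1. Reproduce the plan's figures.** Inputs from section 11.2: difference 33 − 11 = 22, SD 44, so d = 22/44 = 0.5; alpha 0.05; power 80%.
- One-sided test of the cross-reactive clones against a fixed 33%: n = ((1.645 + 0.842)/0.5)² = 24.7, so 25.
- Donors: 25/0.5 = 50; 50 × 1.1 = 55.

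The same formula two-sided gives 32. The unpaired 1:1 comparison gives 63 per group two-sided and 50 one-sided. Power below therefore uses the one-sided, fixed-reference basis, because it returns the plan's 25. It is not the test of section 11.4.

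**2. Range of distinct people.** 15 + 15 + 15 + 10 = 55 slots. With at most three consecutive years, nobody can be in both year 1 and year 4, so there are at least 15 + 10 = 25 people. Distinct people = 55 − R, with R re-enrolments between 0 and 30. (Dividing 55 by 3 gives 19, which ignores the yearly quotas.)

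**3. Clones and power after 10% dropout.** Let f be the clone yield of a repeat enrolment relative to a first one; it is not documented, so 0, 0.5 and 1 are shown. Clones = 0.9 × [0.5 × (55 − R) + 0.5 × f × R]. Power = Φ(0.5 × √clones − 1.645), ignoring correlation.

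| Distinct people | f = 0 (per person) | f = 0.5 | f = 1 (per enrolment) |
|---|---|---|---|
| 55 | 24.75, 80% | 24.75, 80% | 24.75, 80% |
| 45 | 20.25, 73% | 22.5, 77% | 24.75, 80% |
| 35 | 15.75, 63% | 20.25, 73% | 24.75, 80% |
| 25 | 11.25, 51% | 18, 68% | 24.75, 80% |

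With 55 distinct people the count is already a fraction below 25, so on a per-person yield there is no slack.

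**4. Standard error of the clone comparison.** Assumptions, none documented: total variance 1; within-person correlation 0.2 to 0.8; 1 or 5 strain-specific clones per enrolment; a 50% chance of one cross-reactive clone per enrolment. The ratio is true over naive (pooled t-test) standard error, from 20,000 draws.

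| Distinct people (pattern) | Person effect shared by both clone types | Not shared |
|---|---|---|
| 55 (55×1) | 0.69–0.95 | 1.00–1.14 |
| 45 (10×2, 35×1) | 0.69–0.95 | 1.02–1.25 |
| 35 (20×2, 15×1) | 0.69–0.95 | 1.05–1.36 |
| 25 (15×3, 10×1) | 0.69–0.95 | 1.10–1.59 |

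Hand check of the top of the unshared column (correlation 0.8, 5 strain-specific clones per enrolment). The naive variance is 1/27.5 + 1/275 = 0.0400.
- 55 people: 1/27.5 + (1 + 4 × 0.8)/275 = 0.0516; √(0.0516/0.0400) = 1.14.
- 25 people: the strain-specific part is (275 + 0.8 × (15×15² + 10×5² − 275))/275² = 0.0391. The cross-reactive part is (27.5 + 0.8 × 15×6×0.25)/27.5² = 0.0602. √(0.0992/0.0400) = 1.58, against 1.59 simulated.

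**5. Which model repairs it.** In simulation with an unshared effect and 5 strain-specific clones per enrolment, a mixed model with only a person random intercept did worse than the t-test. Its true/model standard-error ratio was 1.42 against 1.06 (55 people, correlation 0.5) and 2.39 against 1.35 (35 people, correlation 0.8). Person-clustered variance stayed at about 0.92 to 1.13 in both the shared and the unshared case.

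**The case against.** **Each re-enrolment is a new vaccination with new marrow samples.** Section 2.1 says of antigenic change: "This requires that the formulation of the influenza vaccine must be updated each season". Repeat enrolments may well yield new clones, and at f = 1 none are lost. This stands as a reason not to assert a shortfall. But section 3.2.3 leaves open whether the same clones re-amplify, and new clones in the same person bring in the correlation.

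**The documents foresee linking years.** The schematic footnote maps later years to day 365 and day 730, and section 8.2.1 gives samples a donor number apart from the study identifier. This also stands. What is missing is a statement that the donor number persists across years, and a rule that the analysis uses it. The Data Management Plan cited in section 11.4 may contain one; it is not among the documents.

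**Stronger readings that a reader might infer, and that are not supported:**
- *That the study has about 25 people.* R is not documented; 25 is only the floor. Enrolment is stated as up to 55, so even 55 filled slots is an assumption.
- *That re-enrolment is why power falls below 80%.* The unpaired two-sided test of section 11.4 has about 46% power with 27.5 against 27.5 clones and 71% with 27.5 against 275, with no re-enrolment and no dropout. That is a separate and larger matter.
- *That re-enrolment makes the t-test too optimistic.* Several clones per donor cause clustering even with 55 distinct people. Re-enrolment adds to it only where the person effect is not shared; where it is shared the test is conservative at every head count.
- *That five re-enrolments can be absorbed, since 55 − 5 = 50.* Those five places are the dropout allowance.

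**Conclusion.** The concern holds. The counting rule does not guarantee the donor number on which section 11.2 rests, and section 11.4 has no rule for several clones or several years from one person.

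The size is conditional. On a per-person yield, any re-enrolment takes the expected clones further below 25 once 10% dropout is applied: 20.25 with 45 people and 15.75 with 35. On a per-enrolment yield the count holds and the issue is independence. The plain standard error may then be too large (ratio 0.69 to 0.95) or too small (up to about 1.14 with 55 people and 1.59 with 25). These figures rest on the reconstructed one-sided basis and on assumed repeat yields, correlations and clones per enrolment; the documents do not say where in these ranges the study lies.

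Severity is moderate. The clonotype-tracking measures are listed as exploratory in section 3.2.3, but the sample size is built on them.

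**What to change.** 1. **Section 11.2.** State the number of distinct people; enrolment closed on March 31, 2020, so it is known. Say whether the 50% yield is per person or per enrolment, and how a clone seen again in the same person is counted. Restate expected clones after dropout, and power, on that head count. Do not offer a re-enrolment tolerance that spends the dropout allowance.
2. **Section 11.4.** Link each person's yearly identifiers, for example through the section 8.2.1 donor number if it stays the same across years. Replace the plain t-test with person-clustered variance and a small-sample correction, or with a mixed model that has both a person effect and a person-by-clone-type effect. Do not use a single person random intercept alone: it understates the standard error when the effect is not shared. Where people give at most one clone of each type, the second random effect cannot be separated from residual error, which favours the clustered variance.
3. **Elsewhere.** Use the same person key in the longitudinal models of section 11 and for the seroconversion percentages of section 3.2.1.

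The cost is a linkage key and wording, with no extra visits or subjects. With enrolment closed, the change corrects what is claimed and cannot enlarge the sample. The stated clone count and power may become less favourable.
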